7. PROCEDURE PLAN

All EUS/FNB and EUS/FNA will be performed using a linear array echoendoscope by one of seven experienced EUS physicians at JHH. All patients will undergo both EUS/FNB and EUS/FNA. Patients will be randomized to either FNB or FNA first by

means of computer-generated numbers. The endoscopist will not be blinded to the randomization; however, the study pathologist will be blinded to randomization.

EUS/FNB will be performed using similar techniques for tissue acquisition as FNA using 22-g FNB needle (Medtronic SharkCore or Boston Scientific Acquire). Lesions will be identified using EUS and punctured with the 22-g FNB needle (10-15 back and forth movements per needle pass, fanning as appropriate). After the lesion is punctured, the stylet will be removed and 10cc suction will be applied. FNB samples will be placed directly into formalin containers and sent to be processed by surgical pathology.

EUS/FNA with ROSE will be performed using standard techniques via 22-g FNA needle (Cook Medical EchoTip Ultra or Boston Scientific Expect or Medtronic Beacon). Lesions will be identified using EUS and punctured with the FNA needle (10-15 back and forth movements per needle pass, fanning as appropriate). After the lesion is punctured, the stylet will be removed and 10cc suction will be applied. FNA specimens will be processed for ROSE using standard techniques with bedside smear slide evaluation and liquid-based cytology and cell-block preparation.

The first randomization assigned EUS sampling technique will be used until adequate specimen is achieved (up to 3 passes total). After 3 passes, the patient will undergo the other EUS sampling technique until adequate specimen is achieved (up to 3 passes total). If inadequate biopsies are obtained after a total of 6 passes (3 with initial tissue acquisition techniques, 3 with the other technique), the endosonographer will be permitted to utilize any EUS sampling technique preferred to obtain a diagnosis during the same procedure or at a later date.

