12. STATISTICAL CONSIDERATIONS

Overview: This study is designed as a non-inferiority trial.

Considering a success rate of 85% in the FNA with ROSE group, based published studies, we selected a non-inferiority margin (∂) of 10%, in accordance with the USFDA recommendations (8). Based on the following formula (9):

n = f(α, β) × [πs × (100 – πs) + πe × (100 – πe)] / (πs – πe – d)2

where πs and πe are the true percent 'success' in the standard and experimental treatment group respectively, and

 $f(\alpha, \beta) = [\Phi - 1(\alpha) + \Phi - 1(\beta)]2$

 Φ -1 is the cumulative distribution function of a standardized normal deviate

We calculated that our trial will require enrolling 120 patients for power of 80% and two sided α of 0.05.

Taking into consideration a 10% dropout rate, the total patients to be enrolled=132

Baseline demographics, pre-, intra- and post-intervention data will be prospectively collected on data collection forms which will be maintained in an electronic database system. Results will be reported as mean ± standard deviation (SD) for quantitative variables and percentages for categorical variables. The groups will be compared using the Student's t- test or Wilcoxon rank sum test for continuous variables and the chi-square test (or Fisher's exact test if required) for categorical variables. To compare

diagnostic accuracy between two EUS sampling techniques, we will use McNemar's test. Statistical significance will be based on two-sided design-based tests evaluated at α = 0.05. All statistical analyses will be performed using STATA.

a. Endpoints:

Primary:

Diagnostic accuracy will be defined as (true positive + true negative)/all samples. The final diagnosis will be based on one of the following criteria: (i) surgical pathology specimen from patients who underwent surgical resection; (ii) cytological or histopathological diagnosis of malignancy in patients with unresectable disease with appropriate imaging and clinical course of disease; (iii) cytological and histopathological diagnosis of benign disease with an appropriate clinical course of disease for minimum of 6 months.

Secondary:

1. Specimen adequacy

This will be defined as the proportion of samples in which a final histopathological diagnosis could be made.

2. Percentage of histology cores obtained

This will be defined as the proportion of samples in which a visible histology core biopsy was obtained

- 3. Number of passes Number of passes required for diagnosis

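### Secondary endpoint 3 asks for passes required for diagnosis, but what the protocol specifies yields only FNB passes performed, and the tests named for it are unpaired

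*Combined protocol and SAP*

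**What the plan says.** Section 12 defines secondary endpoint 3 as "Number of passes required for diagnosis", with no assessor, time point or counting rule. Section 1.3 lists the matching objective simply as number of passes.

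Stopping is governed by Section 7, repeated in Section 8 item e: "The first randomization assigned EUS sampling technique will be used until adequate specimen is achieved (up to 3 passes total". The next sentence reads: "After 3 passes, the patient will undergo the other EUS sampling technique until adequate specimen is achieved (up to 3 passes total".

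The two specimens are handled differently (Section 7):
- FNA: "FNA specimens will be processed for ROSE using standard techniques with bedside smear slide evaluation and liquid-based cytology and cell-block preparation".
- FNB: "FNB samples will be placed directly into formalin containers and sent to be processed by surgical pathology".

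The only definition of adequacy in the document is secondary endpoint 1 in Section 12: "This will be defined as the proportion of samples in which a final histopathological diagnosis could be made". Secondary endpoint 2 counts samples with a visible core; nothing links it to stopping.

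On pairing, Section 7 says "All patients will undergo both EUS/FNB and EUS/FNA". Section 12 names Student's t-test or the "Wilcoxon rank sum test for continuous variables", and names McNemar's test for diagnostic accuracy only.

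**The concern.** To know how many passes a diagnosis required, one needs either a signal in the room that the diagnosis has been secured, or a laboratory result for each pass. FNA can have the first through its bedside smear. For FNB the protocol specifies neither. If FNB stops after two passes and pathology reports a diagnosis, nothing in the protocol shows whether the first pass would have been enough.

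The two counts would then differ in kind: one can respond to the result and the other cannot. Reporting the difference as passes required for diagnosis could credit or blame a needle for the operator's stopping habit. Fewer passes would be a natural message from a trial meant to make tissue acquisition more economical, so the label matters.

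Two further gaps affect the same endpoint. Read literally, the move to the second technique comes only after three passes, which conflicts with stopping at adequacy. And the named tests ignore that each patient supplies both counts.

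**Working it through.** The plan gives no figure for number of passes, so there is none to reproduce. The text settles what can be measured; the arithmetic only shows how far stopping can move the comparison.

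**1. What the text makes available**

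| Needed for passes required | FNA | FNB |
|---|---|---|
| In-room sign | Bedside smear evaluation | None stated |
| Result for each pass | Not stated | Not stated |
| Number of passes taken | Countable | Countable |

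**2. Inputs for the illustration**
- From Section 12: 85% success with FNA and 120 patients, both taken as given. Reading success as yield within three passes is an assumption.
- Assumed: the same per-pass yield p in both techniques, from 0.6 to 0.8; beta-binomial passes with intra-lesion correlation r; FNA stops at its first adequate pass, maximum three.

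**3. Mean FNA passes.** Let q_k be the probability of no diagnostic pass in k:
- q_1 = 1 − p
- q_2 = q_1 × [(1 − p)(1 − r) + r]
- q_3 = q_2 × [(1 − p)(1 − r) + 2r] / (1 + r)

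r is solved so that 1 − q_3 = 0.85. The mean is m = 1 + q_1 + q_2, and the variance is 1 + 3q_1 + 5q_2 − m².

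| p | r | q_1 | q_2 | m | SD |
|---|---|---|---|---|---|
| 0.6 | 0.28 | 0.40 | 0.227 | 1.63 | 0.83 |
| 0.7 | 0.50 | 0.30 | 0.195 | 1.50 | 0.80 |
| 0.8 | 0.79 | 0.20 | 0.166 | 1.37 | 0.75 |

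**4. Gap, FNB minus FNA, with identical needles**

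| FNB passes taken | p = 0.6 | p = 0.7 | p = 0.8 |
|---|---|---|---|
| Always 1 | −0.63 | −0.50 | −0.37 |
| Half 1, half 2 | −0.13 | 0.00 | +0.13 |
| Equally 1, 2, 3 | +0.37 | +0.50 | +0.63 |
| Always 3 | +1.37 | +1.50 | +1.63 |

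The first and last rows are extremes that mark the range. For the equal spread, FNB has variance 2/3. With counts uncorrelated within patient, the standard error is √[(SD² + 0.667)/120] = 0.106, 0.104 and 0.101, so the gap is 3.5, 4.8 and 6.3 standard errors from zero.

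If whichever technique goes first is fixed at three passes and order is 1:1, an FNB mean of k when it goes second gives a gap of (3 + k)/2 − (3 + m)/2 = (k − m)/2. Every gap above is halved.

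**5. Would scoring the first diagnostic pass solve it?** Suppose patients undiagnosed within the passes taken are scored 4. Take p = 0.7 and FNB stopping at one pass. The FNB mean score is 0.7 × 1 + 0.3 × 4 = 1.90. The FNA mean score is 1 + q_1 + q_2 + q_3 = 1 + 0.30 + 0.195 + 0.15 = 1.645. Identical needles still differ by 0.255, because FNA had more attempts. The score still depends on where FNB stops.

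**6. Pairing.** The variance of a within-patient difference is s₁² + s₂² − 2ρs₁s₂. Unpaired tests omit the last term. The documents give no ρ, so the size of the error is unknown.

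**The case against.** The strongest reply is that the protocol leaves detail to other papers. Case report forms are supplied separately (Sections 5 and 10.1), the FNB containers are in the plural, and a visible core, already an endpoint, could serve as an in-room sign. All of this stands to a degree. A reader might infer that the endpoint cannot be measured at all, or that passes are pooled. The documents do not support that: passes may already be kept apart. But separate containers without a read for each pass still do not give the endpoint, and nothing ties the visible core to stopping.

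A reader might also infer that adequacy in the stopping rule means a final histopathological diagnosis. No text links the two, so adequacy there is undefined rather than defined by something unavailable. Likewise, that the FNA smear triggers stopping and that the endoscopist judges FNB adequacy are inferences.

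Comparing passes performed is legitimate, since the trial compares FNB without ROSE with FNA with ROSE as strategies, and Section 1.3 already asks only for number of passes. That is accepted; the trouble lies largely in the added words in Section 12.

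Finally, the groups in the unpaired tests may be the randomised order groups, for which such tests are suitable. That reading is possible, but it leaves no test named for comparing the techniques on passes.

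**Conclusion.** The point holds in limited form: the number of FNB passes required for diagnosis is not obtainable from what the protocol specifies, and the number performed is. A difference in the recorded counts can arise from stopping alone at equal per-pass yield. Under the stated assumptions the gap could lie anywhere from −0.63 to +1.63 passes, including about zero. These figures show dependence on an unspecified habit; they are not an estimate of bias in this trial, and the extremes need every FNB procedure to stop at the same count.

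The unpaired tests do not fit a comparison of techniques within patients, and the three-pass wording conflicts with the adequacy rule. It would be tempting to carry this over to diagnostic accuracy, but no effect on the primary endpoint is shown. It is a minor point on one of five secondary endpoints.

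**What to change.** 1. Section 12: define endpoint 3 as number of passes performed, in line with Section 1.3. Report it as a comparison of strategies and make no claim about passes required for diagnosis. No cost.
2. Section 12: compare it within patient by Wilcoxon signed-rank instead of the t-test or rank sum. No cost.
3. Section 7 and Section 8 item e: move to the other technique after an adequate specimen or three passes, whichever comes first. Name a visible core as the in-room FNB stopping sign. This costs a wording change in two places.
4. Optional, if FNB passes are kept in separately labelled containers: report diagnosis on pass 1 with McNemar's test, using only material attributable to pass 1 in both techniques. This does not depend on where either technique stops. Number the labels within technique, since a running number would show the blinded pathologist the order. State that pooled FNA liquid-based and cell-block material is left out. The cost is pass labels on FNA smears and at most 2 extra FNB containers per patient (2 × 132 = 264), or none if passes are already kept apart, plus smaller specimens to process. This has to be settled before sampling, because pass identity is lost once material is pooled.

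A signed-rank analysis of the first diagnostic pass, with failures given the worst rank, is not recommended, for the reason in step 5 of the working.

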8. PATIENT FOLLOW-UP

All patients will recover from their procedures according to standard practice. They will remain NPO the night after the procedure. After finishing the procedure, all patients will be carefully monitored per standard protocol in the recovery room and be discharged when fully awake and pain-free. Patients will be contacted by telephone at 24-48 hours to ascertain and document any early adverse events that may have arisen. Long-term clinical follow up will be based on clinical indications.

To determine the safety of procedure, all pre, intra- and immediate post-procedure adverse events will be recorded and rated according to ASGE lexicon (7) for adverse events. Inpatients will be evaluated by study coordinator/PI on a daily basis during their hospitalization. Potential complications will be explained for patients at their discharge time and will be advised to refer whenever they have problems.

- a. Study duration and number of study visits required of research participants. Study duration: 2 years Number of subjects: 132 Follow-up visits: 0
- Blinding, including justification for blinding or not blinding the trial, if applicable.
 Due to the nature of study, treatment team will be aware of patient's group and it is not possible to make it double blinded. However, the study pathologist will be blinded to randomization.

- Justification of why participants will not receive routine care or will have current therapy stopped.
 Routine care will be followed
- d. Justification for inclusion of a placebo or non-treatment group. N/A
- e. Definition of treatment failure or participant removal criteria. The first randomization assigned EUS sampling technique will be used until adequate specimen is achieved (up to 3 passes total). After 3 passes, the patient will undergo the other EUS sampling technique until adequate specimen is achieved (up to 3 passes total). If inadequate biopsies are obtained after a total of 6 passes (3 with initial tissue acquisition techniques, 3 with the other technique), the endosongrapher will be permitted to utilize any EUS sampling technique preferred to obtain a diagnosis during the same procedure or at a later date.
- f. Description of what happens to participants receiving therapy when study ends or if a participant's participation in the study ends prematurely. No change in medical care will be expected.

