Fatal Events whether anticipated or unanticipated, and whether or not related to the study must be reported to the Coordinating Center within 24 hours of the participating site Principal Investigator's learning of the event.

Serious and Unanticipated Adverse Events must be reported to the Coordinating Center within 24 hours of the participating site Principal Investigator's learning of the event.

Other Serious Adverse Events which may result in a change to the protocol, informed consent, or risk to subjects as specified in the protocol must be reported within three (3) working days of the participating site Principal Investigator's learning of the event.

Adverse Events which result in no change to protocol, informed consent, or risk to subjects must be reported to the Coordinating Center on a monthly basis.

All SAEs must be collected whether or not they are considered causally related to the investigational procedure. Investigators and other site personnel are responsible for reporting all casually related SAEs to their IRB and the Protocol Chair.

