9.3 Reporting Requirements

Each investigative site will be responsible to report SAEs that occur at that institution to their respective IRB. It is the responsibility of each participating investigator to report serious adverse events to the study sponsor and/or others as described below.

- 9.4 Reporting to the Study Team
 - 9.4.1 Serious Adverse Event Reporting

All serious adverse events that occur after the procedure, during the procedure, or within 30 days of the procedure must be reported to the Principle Investigator on the local institutional SAE form. This includes events meeting the criteria outlined in Section 11.1.2, as well as the following:

- Grade 2 (moderate) and Grade 3 (severe) Events Only events that are unexpected and possibly, probably or definitely related/associated with the intervention.
- All Grade 4 (life-threatening or disabling) Events Unless expected AND specifically listed in the protocol as not requiring reporting.
- All Grade 5 (fatal) Events When the participant is enrolled and actively
 participating in the trial OR when the event occurs within 30 days of the
 last study intervention.
- Progressive disease will be reported within 7 days

Note: If the participant is in long term follow up, report the death at the time of continuing review.

Participating investigators must report each serious adverse event to the overall Principal Investigator within one business day of learning of the occurrence. In the event that the participating investigator does not become aware of the serious adverse event immediately (e.g., participant sought treatment elsewhere), the participating investigator is to report the event within one business day of learning of it and document the time of his or her first awareness of the adverse event.

Report serious adverse events by telephone, email or facsimile to:

[name] [contact] Email: [contact] [contact] Emergency Contact #: [contact] (mobile) Within the subsequent 1-2 business day from initial report, the participating investigator must provide follow-up information on the serious adverse event. Follow-up information should describe whether the event has resolved or continues, if and how the event was treated, and whether the participant will continue or discontinue study participation.

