9.4.2 Non-Serious Adverse Event Reporting

Non-serious adverse events will be not be reported Reporting to the Institutional Review Board (IRB)

Investigative sites should report serious adverse events to their respective IRB according to the local IRB's policies and procedures in reporting adverse events. A copy of the submitted institutional SAE form should be forwarded to:

[name] [contact] Email: [contact] [contact] Emergency Contact #: [contact] (mobile)

- 9.5 Reporting to the Food and Drug Administration (FDA) N/A
- 9.6 Reporting to the NIH Office of Biotechnology Activities (OBA) N/A
- 9.7 Reporting to the Institutional Biosafety Committee (IBC) N/A
- **9.8** Reporting to Hospital Risk Management Participating investigators will report to their local Risk Management office any subject safety reports or sentinel events that require reporting according to institutional policy.
- **9.9** Monitoring of Adverse Events and Period of Observation All adverse events, both serious and non-serious, and deaths that are encountered from initiation of study intervention, throughout the study, and within 30 days of the last study intervention should be followed to their resolution, or until the participating investigator assesses them as stable, or the participating investigator determines the event to be irreversible, or the participant is lost to follow-up. The presence and resolution of AEs and SAEs (with dates) should be documented on the appropriate case report form and recorded in the participant's medical record to facilitate source data verification.

For some SAEs, the study sponsor or designee may follow-up by telephone, fax, and/or monitoring visit to obtain additional case details deemed necessary to appropriately evaluate the SAE report (e.g., hospital discharge summary, consultant report, or autopsy report).

Participants should be instructed to report any serious post-study event(s) that might reasonably be related to participation in this study. Participating investigators should notify the Overall Investigator or respective IRB of any unanticipated death or adverse event occurring after a participant has discontinued or terminated study participation that may reasonably be related to the study.

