- 4. Rate of technical failures

Technical failure was defined as the inability to perform the procedure, including the need to change the needle

5. Adverse events

All pre, intra- and immediate post-procedure adverse events will be recorded and rated according to ASGE lexicon for adverse events.

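### The protocol sets a 30-day adverse event window, but the last scheduled contact after discharge is at 24-48 hours and the endpoint counts only undefined immediate events, so later events can be missed.

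*Combined protocol and SAP*

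**What the plan says.** **Window.** Section 9.4.1 states: "All serious adverse events that occur after the procedure, during the procedure, or within 30 days of the procedure must be reported". Section 9.9 applies the same horizon to serious and non-serious events alike. Those encountered up to or "within 30 days of the last study intervention should be followed to their resolution", or until they are judged stable or irreversible or the patient is lost to follow-up.

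**Ascertainment.** Section 8 provides one contact after discharge: "Patients will be contacted by telephone at 24-48 hours to ascertain and document any early adverse events that may have arisen". It also states "Follow-up visits: 0" and "Long-term clinical follow up will be based on clinical indications". Inpatients are reviewed daily, and patients are told at discharge to come back if they have problems. Section 9.2 has investigators assess events at the participant evaluation time points.

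**Endpoint.** Secondary endpoint 5 in section 12 reads: "All pre, intra- and immediate post-procedure adverse events will be recorded and rated according to ASGE lexicon for adverse events". Section 8 says nearly the same. Neither place defines *immediate*.

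**Reporting.** Under section 6, adverse events that change nothing in the protocol, consent or risk "must be reported to the Coordinating Center on a monthly basis". Section 9.4.2 says: "Non-serious adverse events will be not be reported".

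**The concern.** The safety window, the contact schedule and the endpoint describe three different periods. A coordinator following section 8 has no scheduled reason to ask a discharged patient about adverse events after day 2. An analyst following section 12 cannot tell whether an event on day 2 or day 7 counts.

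This matters because adverse events are a stated secondary objective (section 1.3), and section 8 says they are recorded to establish the safety of the procedure. Under section 7 every patient is sampled with both techniques, up to three passes each, and further sampling is allowed if six passes fail. Section 8.1 names infection and pancreatitis as risks without a frequency for either, so the trial's own count is the evidence it will offer. Section 8.1 also has pancreatitis detected through symptoms, which after the call depends mainly on the patient coming forward. The DSMB (section 10.2) can review only what the sites learn of.

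**Working it through.** The plan states no figure to reproduce here. The check is a comparison of sections, followed by a labelled illustration.

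**1. Sections side by side**

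| Element | Source | Period covered |
|---|---|---|
| Serious event reporting | 9.4.1 | to day 30 |
| Observation of all events | 9.9 | onset to day 30, then followed to an outcome |
| Scheduled contact after discharge | 8 | one call at 24-48 hours |
| Follow-up visits | 8 | none |
| Adverse event endpoint | 12, also 8 | before, during and immediately after the procedure; no end point in time |

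**2. Share of the window without a scheduled check.** The call is at day 2 at the latest: 30 − 2 = 28 days, and 28/30 = 93%.

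**3. Could another planned contact fill the gap?** Section 13 ties the DSMB's 50% analysis to an initial outpatient follow-up, but no such visit is defined and section 8 gives zero. The six-month clinical course in section 12 supports a benign final diagnosis and is not an adverse event contact. Neither closes the gap as written.

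**4. What the documents say about frequency.** Section 8.1 gives bleeding as 1 in 5,000, so 132 × 1/5,000 = 0.026 expected bleeds. It gives perforation as below 1%, so fewer than 132 × 0.01 = 1.32. It gives no figure for infection, for pancreatitis, for all events together, or for the share arising after 48 hours.

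**5. Illustration only.** Assume a true 30-day rate r of 1% to 3%, and a share s of 25% to 75% of events that arise after the call and go uncaptured. Neither range comes from the documents. Expected observed events = 132 × r × (1 − s).

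| r | True expected | Observed, s = 25% | Observed, s = 75% |
|---|---|---|---|
| 1% | 1.32 | 0.99 | 0.33 |
| 3% | 3.96 | 2.97 | 0.99 |

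The chance of seeing at least one event is 1 − (1 − r(1 − s))^132. At r = 1% it is 1 − 0.99^132 = 74% with full capture, 63% at s = 25% and 28% at s = 75%.

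**6. Precision with few events.** With 0 events in 132 patients, the one-sided 95% upper bound is 1 − 0.05^(1/132) = 2.2%. The exact one-sided bounds for 1 and 2 events are 3.5% and 4.7%. If an event were lost, the safety statement would shift noticeably. This does not show that one would be lost.

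**The case against.** The strongest reply is that a peri-procedural endpoint may properly sit beside a longer safety-reporting window. Section 12 does not claim a 30-day rate, so a rate labelled as immediate would not misstate one. That stands as a matter of design. It does not supply the missing definition of *immediate* or give section 9.9 a means of ascertainment.

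A reader might infer that late events will be missed, or will surface only if patients volunteer them. The documents do not support this. Section 9.2 records events found by questioning, examination, laboratory test or other means; inpatients are seen daily; section 9.4.1 provides for events treated elsewhere and learned of later; and section 9.9 asks patients to report serious, possibly related events after the study. These routes are partial, and for discharged patients after the call they are unscheduled, so the supportable wording is that late events can be missed.

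A reader might also put a size on the loss. Suppose 20-50% of events arise after 48 hours and half go unreported: the under-count is 0.2 × 0.5 = 10% to 0.5 × 0.5 = 25%. Both inputs are unsupported, and at a 1% rate the product is only 1.32 × 0.10 = 0.13 to 1.32 × 0.25 = 0.33 of an event. Losing one event on average would need 1/0.25 = 4 to 1/0.10 = 10 true events, or 3.0% to 7.6% of 132 patients.

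On non-serious events, sections 9.2 and 9.9 already put them on case report forms, and section 5 sends those forms to the Coordinating Center. The data path therefore largely exists. What remains is the conflict in wording between sections 6 and 9.4.2, which a site cannot satisfy together.

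**Conclusion.** The mismatch is real and should be corrected. As written, discharged patients have no scheduled adverse event check for about 28 of the 30 days the protocol says it covers, and the endpoint has no defined end. Later events can be missed, and the overall adverse event rate can be understated. This rests on section 8 being the complete contact schedule and on sites following it as written.

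The size of any understatement cannot be estimated from the documents; the illustration shows direction only.

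Two stronger readings should be set aside. One is that the gap biases FNB against FNA: section 7 gives every patient both techniques, so under-ascertainment acts mainly on the overall rate, and no difference between techniques is shown. The other is that it weakens the main result: the primary endpoint, diagnostic accuracy, does not depend on adverse event capture. The point concerns a secondary endpoint and is a should-fix on that footing.

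**What to change.** 1. Add one scripted adverse event check at day 30, by telephone or chart review, using the same questions as the 24-48 hour call. Record which source was used, since chart review alone can miss events treated elsewhere.
2. Define secondary endpoint 5 in section 12 as adverse events from the procedure to day 30, with the 24-48 hour count shown separately. Align the parallel sentence in section 8.
3. Reconcile section 6 (monthly reporting) with section 9.4.2 (no reporting of non-serious events), so that sites have one instruction.
4. Reconcile the outpatient follow-up mentioned in section 13 with the zero visits in section 8.

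The cost is about 132 short contacts by existing coordinators and one case report form page. Sample size, procedures and the primary analysis are unchanged.
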